7.5 Efficacy and Pharmacokinetic Assessments

For all subjects, blood samples for pharmacologic (efficacy and safety) assessments will be drawn at all visits except Screening (Table 1). All blood samples should be drawn in a fasted state (approximately 10 hours). Instructions for collecting, processing, storing and shipping of blood samples for pharmacologic and pharmacokinetic analyses will be provided in the Laboratory Manual.

Blood samples for trough PK analysis of MSDC-0602 and MSDC-0597 will be collected pre-dose at Study Visits 2, 4, 5, 6 and 7 (Days 30, 90, 180, 270 and 360).

Blood samples for analysis of FPG and HbA1c will be collected at Screening.

Blood samples for analysis of insulin, HOMA-IR, FPG, HbA1c, TG, FFA and fasting cholesterol (total, HDL, LDL, VLDL) will be collected as part of the standard chemistry profile at Study Visits 1, 5, and 7 (Days 1, 180 and 360).

Blood samples for analysis of liver function tests (AST, ALT, bilirubin, PT/INR, ALP, GGT and albumin) will be collected at Study Visits 1, 2, 3, 4, 5, 6 and 7 (Days 1, 30, 60, 90, 180, 270 and 360).

Blood samples for analysis of HMW adiponectin, hsCRP, osteocalcin, serum CTX concentrations will be collected at Study Visits 1, 5, and 7 (Days 1, 180, and 360).

Blood samples for biomarkers of liver apoptosis (CK-18 [M30 and M65]) will be collected at Visits 1, 5 and 7 (Days 1, 180, and 360), whereas blood samples for TIMP-1, PIIINP, HA will be collected at Visits 1 and 7 (Days 1 and 360).

Serum samples for NMR analysis of lipoprotein particle size will be collected at Study Visits 1 and 7 (Days 1 and 360).

Blood samples will be collected at Visit 1 (Day 1) to be analyzed for genotyping.

Plasma samples for future miRNA measurements and additional biomarkers of interest will be collected at Study Visits 1, 5 and 7 (Days 1, 180 and 360).

Data obtained from the circulating liver function tests and other biomarkers will be used to calculate composite scores that may provide an indirect measure of changes in fibrosis from baseline to the 12 month endpoint (Days 1 and 360).

It is estimated that approximately 226 mL of blood for the safety, pharmacokinetic, and pharmacodynamic parameters will be drawn from each subject who completes the trial.

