2.2 Overall Study Design

This is a randomized, double-blinded, placebo-controlled multiple-dose phase II study to evaluate the safety, tolerability and efficacy of three dose levels of MSDC-0602K in subjects with non-alcoholic steatohepatitis (NASH).

Approximately 380 subjects will be randomized at 1:1:1:1 ratio to the following four treatment arms, and the drug is taken orally once per day for 12 months:

- MSDC-0602K 62.5 mg
- MSDC-0602K 125 mg
- MSDC-0602K 250 mg
- Placebo

Randomization will be stratified by:

- Presence of Type 2 diabetes mellitus (T2DM) (Yes/No)
- Use of Vitamin E \geq 400 IU (Yes/No)
- Fibrosis score (F1 vs. F2/F3)

This study will comprise a maximum 42-day Screening period, a treatment period of 360 days and a 14-day follow-up period. The total duration of the study for each subject will be up to 416 days, including follow-up.

The primary efficacy endpoint will be assessed at 12 months after randomization. Visits to the clinic will be at baseline, 1, 2, 3, 6, 9, and 12 months, with one follow-up visit at study day 374.

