2.3 Sample Size and Power

Each active treatment group will be compared with the placebo group at the two-sided 0.05 significance level; 85 subjects per arm provides approximately 80% power to detect a difference in the proportions of subjects achieving the primary efficacy endpoint of 39.5% in any MSDC-0602K group versus 20% response rate in the placebo group. These response rates are similar to effects reported after 18 months daily treatment with 45 mg pioglitazone (58% response) or placebo (17% response) in subjects with pre-diabetes or T2DM (Cusi 2014); after 96 weeks daily treatment with 30 mg pioglitazone (34% response) or placebo (19%) in non-diabetic adults with NASH in the PIVENS study (Sanyal 2010); and in the GOLDEN study, after 52 weeks daily

treatment with 120 mg elafibranor (32% response) or placebo (21%) in the subset of NASH subjects with a baseline NAS ≥ 4 (Ratziu 2016). Assuming 10% of subjects will not complete the 12-month assessment due to early dropout, 380 subjects will be randomized to the study. Sample size calculations were made using nQuery Advisor® (Statistical Solutions Ltd., Boston, MA, USA).

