6.2.4 Imputation for Missing Changes in Laboratory Values

HbA1c

Additional sensitivity analyses may be performed conditional on the distribution of changes in glycemic control medications between the placebo and active treatment groups at 6 and 12 months.

If more than 35% of the subjects who had a major up-titration of glycemic control medications are in the placebo group, a sensitivity analysis may be done where the 6- and 12-month values of HbA1c for subjects who had a major up-titration of glycemic control medications will be imputed to be 0.5 % higher than the observed value.

If more than 15% of the subjects who had a major down-titration of glycemetic control medications are in the placebo group, a sensitivity analysis may be done where the 6- and 12-month values of HbA1c for subjects who had a major down-titration of glycemetic control medications will be imputed to be 0.5 % lower than the observed value.

If more than 35% of the subjects missing paired change-from-baseline values of HbA1c (separately at 6 and 12 months) are in the placebo group, a sensitivity analysis may be performed where the missing follow-up value will be assigned the baseline value plus 0.5%.

Liver function tests and other markers

Additional sensitivity analyses may be performed conditional on the distribution of missing values between the placebo and active treatment groups at 6 and 12 months.

If > 35% of the subjects missing paired change-from-baseline values of the following laboratory tests (separately at 6 and 12 months) are in the placebo group, a sensitivity analysis may be performed where missing follow-up values will be assigned the corresponding baseline values plus 0.5 times the maximum change (maximum increase) from baseline for the parameter observed in any subject (i.e., regardless of treatment group) at the timepoint: ALT, AST, ALP, Total Bilirubin, GGT, pro thrombin time, APRI score, CK-18, ELF, FIB-4, Pro-C3, Fibro-test score, and HOMA-IR. Likewise for albumin, missing follow-up values may be assigned the corresponding baseline values minus 0.5 times the minimum change (maximum decrease) from baseline .

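### The optional missing-value check for liver and other markers adds half of the single largest rise, and opens only when placebo is missing more, so together these tilt it towards the drug

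*SAP*

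**What the plan says.** SAP 6.2.4, under liver function tests and other markers, starts with a trigger: "If > 35% of the subjects missing paired change-from-baseline values of the following laboratory tests" are in the placebo group, judged separately at 6 and 12 months, a sensitivity analysis may be run. Missing follow-up values, in any arm, are then set to baseline plus "0.5 times the maximum change (maximum increase) from baseline for the parameter observed in any subject". The maximum is taken over all arms for that parameter at that timepoint. The section gives no cap, percentile, outlier rule or variance allowance, and no matching rule for more missing data on active treatment. The 13 markers treated this way are ALT, AST, ALP, total bilirubin, GGT, prothrombin time, APRI, CK-18, ELF, FIB-4, Pro-C3, Fibro-test and HOMA-IR. Albumin has a mirrored rule, which is not part of this point.

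These are exploratory endpoints (SAP 3.3). SAP 7.8.4 compares each dose with placebo by ANCOVA, log-transforms highly skewed variables, and presents log-scale results for ALT, AST, ALP and GGT whatever their skewness.

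Protocol 7.5 says that blood for liver function tests "will be collected at Study Visits 1, 2, 3, 4, 5, 6 and 7". CK-18 and the inputs to HOMA-IR are scheduled only at Visits 1, 5 and 7. The Protocol's schedule of activities gives the same three visits for Fibrosure, ELF and Pro-C3.

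**The concern.** Adding an unfavourable change to missing subjects looks like a cautious stress test. It would be cautious if the penalty fell mainly on the active arms. Here it applies to all arms, and the analysis opens only when placebo holds well over its expected quarter of the missing subjects. A rise is unfavourable for all 13 markers, so the penalty falls mainly on placebo and makes the drug look better.

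The size of the penalty has no planned meaning, because one flare in one subject fixes it. It is applied once, with no imputation variance. It also sets aside data already collected: a subject who misses the 12-month visit may have liver tests from Visits 2 to 6. At stake is whether this analysis, if run and reported, can be read as evidence that the marker results are robust to missing data.

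**Working it through.** **Plan's own figures.** The SAP gives no figure for this rule. The counts below rest on its sample size: "85 subjects per arm provides approximately 80% power to detect a difference in the" primary response rates, "39.5% in any MSDC-0602K group versus 20% response rate in the placebo group". The uncorrected two-sided two-proportion formula at 85 per arm gives 79.96% power, which reproduces it. The inflation also holds: 340 / 0.90 = 378, or about 380.

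**Inputs from the documents.** "Approximately 380 subjects will be randomized at 1:1:1:1 ratio", so 380 / 4 = 95 per arm and placebo is expected to hold 25% of missing subjects. "Assuming 10% of subjects will not complete the 12-month assessment due to early dropout, 380 subjects will be randomized to the study", so 0.10 × 380 = 38 missing.

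**Assumptions, not in the documents.** The largest rise M, and the split of missing subjects between arms. For the simulations also: ALT-like baseline, lognormal with median 55 U/L and log-SD 0.45; log-scale residual SD 0.35; no treatment effect; missingness random within arm.

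**Step 1: when the rule opens.** 13/38 = 34.2% does not trigger; 14/38 = 36.8% does. That leaves (38 − 14)/3 = 8 per active arm. If missingness is unrelated to arm, the hypergeometric probability of 14 or more on placebo is 6.1%. With 20 missing in total it is 9.6%, and with 57 it is 4.4%.

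**Step 2: shift in placebo minus active.** Taking the true mean change as about zero:

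shift = (m_placebo − m_active)/95 × 0.5 × M

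With 40% of 38 on placebo: 15.2 versus 22.8/3 = 7.6, so (15.2 − 7.6)/95 = 0.08 and the shift is 0.08 × 0.5 × M.

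| Missing, placebo vs each active arm | M = 100 | M = 200 | M = 300 | M = 400 |
|---|---|---|---|---|
| 14 vs 8 | 3.2 | 6.3 | 9.5 | 12.6 |
| 15.2 vs 7.6 | 4 | 8 | 12 | 16 |
| 17 vs 7 | 5.3 | 10.5 | 15.8 | 21.1 |

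(U/L, favouring the drug; zero when the counts are equal.)

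**Step 3: why a larger outlier need not mean significance.** The constant also widens the spread within each arm. As M grows, a dose–placebo comparison tends to a comparison of missing fractions:

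z = (p_P − p_A) / √[(p_P(1 − p_P) + p_A(1 − p_A))/95]

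For 14 vs 8: 0.0632 / √[(0.1257 + 0.0771)/95] = 1.37. For 16 vs 8 it is 1.76, and for 17 vs 7 it is 2.21. Only the last exceeds 1.96.

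**Step 4: simulated false-positive rate per dose comparison**, baseline-adjusted ANCOVA, nominal 5%. The three figures are for no added outlier (largest rise about 95 U/L), a 300 U/L rise and a 500 U/L rise.

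| Missing | Raw scale | Log scale |
|---|---|---|
| 9 vs 9 | at most 2.3%, no bias | at most 2.3%, no bias |
| 14 vs 8 | 8.9 / 7.2 / 5.2% | 8.6 / 9.1 / 8.8% |
| 17 vs 7 | 26 / 60 / 74% | 21 / 43 / 52% |

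ANCOVA on the observed data alone stayed at 3.5 to 5.8%. Across all runs, 14 vs 8 gave about 4 to 9%.

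At 16 vs 8 (16/40 = 40% on placebo), with a maximum up to 400 U/L, the rate was 11 to 20% raw and 13 to 20% log, essentially all favouring the drug. On recheck, that range matches fitting each dose–placebo pair separately. One model across four arms pools the residual variance with arms that have fewer imputed values and gives more: 16.5% with no outlier, 25% at 300 and 31% at 500 U/L (raw).

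**Step 5: smaller increment.** At 16 vs 8, replacing half the maximum by 0.5 SD of the observed change brought the rate to about 5 to 8%. With a 400 U/L outlier present, the false shift was about 1.2 U/L.

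**The case against.** A reader might infer that one outlier by itself can create a treatment difference. It cannot. With equal missingness there is no bias and the test becomes conservative. At the minimum trigger, raw-scale rejection falls as the outlier grows. At 16 versus 8, an ordinary maximum with no flare already inflates the error rate. The distortion is joint: the placebo-only trigger supplies the imbalance and the direction, and the increment supplies the size. This part of the objection stands in full.

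A reader might also infer that the check is worthless, or that it puts the trial's conclusions in doubt. The documents support neither. Penalising missing values is a recognised stress test, and the quarrel is with its size and with when it is used. The analysis is optional and concerns exploratory markers only. If missingness is unrelated to arm, it opens about 6% of the time with 38 missing.

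Two further limits stand. The planned log-scale analysis softens the effect at larger imbalance but does not remove it. The argument about unused repeat visits holds for liver function tests. For markers scheduled only at Visits 1, 5 and 7 there is no earlier post-baseline value at 6 months.

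What remains is that nothing in the documents caps the increment. The SAP also does better nearby: section 6.2.3 uses multiple imputation with Rubin's rules for the primary endpoint, and the HbA1c rule for missing values uses a fixed 0.5%.

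**Conclusion.** The point holds as a minor one. When the rule opens, unequal missingness and an increment set by one observation together bias these comparisons towards the drug. The shift formula is arithmetic. The 4, 8 and 16 U/L figures depend on the SAP's 10% dropout, an assumed 40% placebo share of the missing, and an assumed maximum rise.

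The false-positive rates rest further on the assumed ALT-like distribution and on how the ANCOVA is fitted. They are about 4 to 9% at the minimum trigger, 11 to 20% at 16 versus 8 (up to about 31% in a four-arm model with a 500 U/L rise), and roughly 20 to 60% at 17 versus 7 for a maximum up to 300 U/L. They illustrate the mechanism and do not forecast this trial. The low chance of opening assumes that missingness is unrelated to arm; if placebo subjects leave more often, the rule opens more often.

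**What to change.** In SAP 6.2.4, replace the half-maximum rule with multiple imputation by arm. Impute on the scale of that marker's ANCOVA: log for ALT, AST, ALP, GGT and other highly skewed markers. Use baseline, earlier post-baseline values where collected, the stratification factors, age and sex, and combine by Rubin's rules.

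For a pessimistic version, add a pre-stated delta of 0.5 SD of the observed change at that visit, in the unfavourable direction for the marker. State in the SAP that a common delta still shifts the comparison slightly when missingness is unequal.

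The cost is one reworded paragraph and modest extra programming. The change should be made before unblinding for the final analysis.

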11.1 Sample Size and Power Calculations

Each active treatment group will be compared with the placebo group at the two-sided 0.05 significance level; 85 subjects per arm provides approximately 80% power to detect a difference in the proportions of subjects achieving the primary efficacy endpoint of 39.5% in any MSDC-0602K group versus 20% response rate in the placebo group. These response rates are similar to effects reported after 18 months daily treatment with 45 mg pioglitazone (58% response) or placebo (17% response) in subjects with pre-diabetes or T2DM (32); after 96 weeks daily treatment with 30 mg pioglitazone (34% response) or placebo (19%) in non-diabetic adults with NASH in the PIVENS study (34); and in the GOLDEN study, after 52 weeks daily treatment with 120 mg elafibranor (32% response) or placebo (21%) in the subset of NASH subjects with a baseline NAS ≥ 4 (35). Assuming 10% of subjects will not complete the 12-month assessment due to early dropout, 380 subjects will be randomized to the study.

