3.3 Exploratory Efficacy Endpoints

Exploratory efficacy endpoints include the following:

- Mean change from baseline relative to placebo at 12 months in liver stiffness as measured using the FibroScan device
- Change from baseline relative to placebo for liver function tests (ALT, AST, ALP, GGT, bilirubin, albumin, PT and INR), normalization of ALT and AST, and changes from baseline relative to placebo for biomarkers and indirect measures of apoptosis and liver fibrosis (CK-18 [M65], Fibrosure, APRI, FIB-4 index, Pro-C3, and ELF score and its individual components TIMP-1, PIIINP, HA) at 6 and 12 months.

- Changes from baseline relative to placebo in circulating inflammatory markers (HMW adiponectin and hsCRP) and markers of bone metabolism (osteocalcin and serum CTX) at 6 and 12 months.
- Changes from baseline relative to placebo in FFA, serum triglycerides, and fasting cholesterol (total, HDL, LDL, VLDL) at 6 and 12 months, and changes from baseline in NMR analysis of lipoprotein particle size at 12 months.
- Changes from baseline relative to placebo in markers of insulin sensitivity: HOMA-IR, HbA1c, fasting plasma glucose, and fasting insulin at 6 and 12 months.
- Changes from baseline relative to placebo in blood pressure (systolic and diastolic), heart rate, weight, and abdominal girth at 6 and 12 months.
- Changes from baseline relative to placebo at 12 months in the central pathologist's general impression of NASH diagnosis: 1) Confirmed, or 2) Cannot be confirmed.

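### Read literally, the albumin sensitivity imputation in SAP 6.2.4 has a sign error: it gives missing subjects a rise where the parallel rule implies a fall (minor)

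*SAP*

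**What the plan says.** SAP 6.2.4, under liver function tests and other markers, allows a sensitivity analysis that depends on where the missing data fall: "If > 35% of the subjects missing paired change-from-baseline values of the following laboratory tests (separately at 6 and 12 months) are in the placebo" arm. For ALT, AST, ALP, total bilirubin, GGT and the other listed markers, a missing follow-up value is then "assigned the corresponding baseline values plus 0.5 times the maximum change (maximum increase) from baseline for the parameter observed in any subject", whatever the arm, at that timepoint.

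Albumin has its own sentence, joined to that rule by its first word: "Likewise for albumin, missing follow-up values may be assigned" a value built the other way round. The instruction is that "missing follow-up values may be assigned the corresponding baseline values minus 0.5 times the minimum change (maximum decrease) from baseline".

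Both rules are permissive: the analysis may be done, and the albumin values may be assigned. Albumin is an exploratory efficacy marker in SAP 3.3: "Change from baseline relative to placebo for liver function tests (ALT, AST, ALP, GGT, bilirubin, albumin, PT and INR". I found no other place in either document that restates or corrects the albumin rule, and SAP section 8 does not mention it.

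**The concern.** For the other markers the rule adds half of the largest increase, so a subject with a missing value is assumed to have worsened. The mirror image for albumin should assume a fall. To get there, the SAP changed two things: the statistic (maximum to minimum change) and the operator (plus to minus). Either change could give a fall under a suitable sign convention. On a signed scale the two cancel and albumin goes up.

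If this is programmed literally, one marker in the set is imputed in the opposite direction from the rest. If the sign is queried only after unblinding, the choice between the two versions is made with the data in view.

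**Working it through.** The SAP gives no numerical result for this rule, so there is no figure to reproduce. The check is on the sign, followed by an illustration of size.

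**Sign.** Let change = follow-up - baseline, and let D > 0 be the largest decrease in any subject, so that the minimum change is -D.

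- Other markers: baseline + 0.5 × (maximum change). The operand is a signed increase, so the value rises.
- Albumin, literal: baseline - 0.5 × (-D) = baseline + 0.5D. The value rises.
- Albumin, as the parallel implies: baseline + 0.5 × (-D) = baseline - 0.5D. The value falls.
- Gap per imputed subject: 0.5D - (-0.5D) = D.

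The operand has to be signed for the text to make sense. A minimum change can be the same thing as a maximum decrease only on a signed scale; on an absolute scale the minimum change would be the smallest movement. The minimum is also a standard summary statistic in SAP 7.1, so a programmer who takes it from the change variable will get a negative number.

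**Size for one subject.** The documents give no albumin distribution. I assume a baseline of 42 g/L and vary D.

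| D (g/L) | Literal: 42 + 0.5D | Implied: 42 - 0.5D | Gap |
|---|---|---|---|
| 4 | 44 | 40 | 4 |
| 8 | 46 | 38 | 8 |
| 12 | 48 | 36 | 12 |
| 16 | 50 | 34 | 16 |

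**Size at arm level.** SAP 2.2 gives the design: "Approximately 380 subjects will be randomized at 1:1:1:1 ratio to the following four treatment arms", so 380 / 4 = 95 per arm. Protocol 11.1 gives the dropout: "Assuming 10% of subjects will not complete the" 12-month assessment. Taking that 10% as the share with missing albumin is my assumption, and gives 38 subjects. The smallest whole number on placebo that meets the trigger is 14 (14/38 = 36.8%; 13/38 = 34.2% falls short). I divide the remaining 24 equally, 8 per active arm.

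The imputed subjects' contribution to the unadjusted active-minus-placebo mean change is (8/95 - 14/95) × imputed change = -(6/95) × imputed change. The imputed change is +0.5D under the literal rule and -0.5D under the implied one.

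| D (g/L) | Literal (g/L) | Implied (g/L) |
|---|---|---|
| 4 | -0.13 | +0.13 |
| 8 | -0.25 | +0.25 |
| 12 | -0.38 | +0.38 |
| 16 | -0.51 | +0.51 |

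The analysis runs only when missing values are concentrated on placebo. In this illustration the literal rule therefore pulls active minus placebo down at every D, where the implied rule would push it up.

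**The case against.** The best defence is that the sentence can be read correctly. The operand is glossed in brackets as a maximum decrease, and a decrease is commonly quoted as a positive size. Subtracting half of a positive 8 g/L gives the intended fall. The linking word, the switch of operator and the switch from increase to decrease all point the same way, so a careful programmer may well recover the intent. This stands as far as it goes, and it is why the point is limited to the literal reading. It does not remove the problem, because the operand actually named is the minimum change, and two programmers could reasonably differ. It also has to be said that the intended fall is an inference; the SAP does not state the direction outright.

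The second defence is that very little depends on this. That also stands. Under SAP 6.2, missing data are left unimputed except where 6.2.1 to 6.2.4 provide otherwise, so the main albumin comparison is the ANCOVA in SAP 7.8.4 without this imputation. The primary endpoint has its own imputation in 6.2.3.

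A reader might go further and infer that missing subjects get a best-case albumin. The text does not support that: they get a rise equal in size to the fall that was implied, which is not the largest increase observed.

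**Conclusion.** The sign error is real on the literal text, and it is minor. It is worth D per imputed subject and reverses the sign of the imputed subjects' contribution to the between-arm difference. Under the assumptions above, that is about -0.13 to -0.51 g/L for active minus placebo where +0.13 to +0.51 g/L was intended. The sign result needs only that at least one subject's albumin falls. The sizes rest on assumed values of D and an assumed split of missing subjects.

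It may be tempting to conclude that the albumin treatment comparison itself reverses, or that the albumin result would contradict those for the other liver tests. Neither follows. Only the imputed part changes sign; the whole estimate also depends on the observed difference between arms, which the documents do not give. The analysis is optional, runs only if the placebo share of missing subjects exceeds 35%, and covers one exploratory marker. The primary endpoint, the secondary endpoints and the sample size are untouched.

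**What to change.** Amend the albumin sentence in SAP 6.2.4 in one of two equivalent ways: *baseline value plus 0.5 times the minimum (most negative) change from baseline seen in any subject at that timepoint*, or *baseline value minus 0.5 times the absolute value of the maximum decrease*. It would help to add that the purpose is to impute a fall in albumin, so that the direction is stated and need not be inferred. The cost is a few words, with no new data and no extra analysis. It should be done before unblinding for the final analysis, so that the sign is not chosen with the results in view.
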